The objective of this study is to test the repellent efficacy characteristics of the test materials to mosquitoes. The active ingredient, KBR 3023 (aka Icaridin; Picaridin), is of known high broad spectrum efficacy, but has not been studied at very many concentrations in the United States.

Note that efficacy will be measured as Complete Protection Time. Complete Protection Time, or CPT, is defined herein as the time between application of test material and the First Confirmed 'Lite with Intent to Bite.' A 'Lite with Intent to Bite', or 'LIBe', occurs when a mosquito alights on the treated test skin of a subject and extends its proboscis to the skin surface while ceasing locomotion. A 'First Confirmed LIBe' is that which is followed by another within 30 minutes. The work conducted pursuant to this protocol will be initiated by determining the amount of each of the repellents that subjects typically apply. Dosimetry will consist of a behavioral assay.

5.2 Rationale and Main Endpoint:

Existing efficacy data on KBR 3023 has been developed over several years by Bayer/Lanxess sponsored studies, independent researchers, World Health Organization (WHO) and military research organizations of the United States and Australia. Twenty percent formulations were found to have efficacy of 8 hours against numerous species and under a variety of climatic condition in various parts of the world. However, LANXESS does not have efficacy data generated in the United States. As part of the registration review of the 20% formulations, US EPA has requested new, US-based efficacy data as condition of registration. The rationale for this study is to provide those efficacy data. The information will also be used in product labeling and for increased user acceptance.

This study will test the efficacy of two newly registered formulations of KBR 3023 that are intended to provide information on Complete Protection Time achieved by a single application of the product. KBR 3023-based repellents have been marketed around the world for a decade, but the product is comparatively recent in the United States market (2005). The US Centers for Disease Control has acknowledged the existence of substantial consumer interest in new and effective insect repellent products, and that KBR 3023-based repellents are among the very few of sufficiently high efficacy to offer reliable personal protection against vectors of West Nile Virus (in April 2005). However, few 'Picaridin' products are currently marketed in the US. Thus there is substantial merit in the development and unconditional registration of new KBR 3023-based repellent products.

Information regarding the stability of the end-products is available from the sponsor in a separate study.

The main endpoint of this study will be the conclusion of a mosquito repellent efficacy field test of novel KBR 3023-based topical repellent formulations (KBR 3023 All-Family Insect Repellent Spray and KBR 3023 All-Family Insect Repellent Cream), with the data set suitable for submission to US/EPA to comply with the conditions of the registration. The efficacy study will consist of two field trials. In each trial, the Picaridin formulations will be tested with 10 subjects, with two untreated control subjects. Initial dosage determination ('dosimetry') will also be conducted with 10 subjects per formulation, some of whom may then go on to participate in efficacy testing. Dosimetry will be conducted at the letterhead address. When 10 subjects have completed dosimetry for each formulation, the resulting data will be used to determine dosing for the efficacy testing.

5.3 Rationale for use of Human Subjects:

Human subjects are required because they represent the target system for the test material, and sufficiently reliable models for repellency testing have not been developed. In addition, subjects will self-administer the test articles during dose determination. Ten subjects are required in order to reduce variation around the population means we will describe.

5.4 Balance of Risks and Benefits:

The study-associated risks are of three types: exposure to the test materials themselves, exposure to biting arthropods, and possible

exposure to vectors of arthropod-borne diseases. As described below, subject health and safety are unlikely to be impacted by any study-associated risks during or after the study.

The repellent active ingredient has a low acute and chronic risk profile, established both through experimentation and through a history of consumer use. The concentration of the active ingredient in the product being tested is lower than that of other products currently EPA-registered and marketed in the US. Subjects with known allergic reactions to insect repellents and common cosmetics are excluded from participating. 'Repeat' exposures during dosimetry are all of brief duration before the product is washed off, and the likely total exposure time is much shorter than a typical single consumer application. Risks associated with inhalation and ingestion would only ensue from serious mishandling by subjects, a scenario that the study methods preclude. The summary toxicology profile of KBR 3023 is appended.

The risk of skin reactions to a mosquito bite is reduced by excluding candidate subjects who are aware of having a history of such reaction. In addition, subjects will be trained to quickly remove any mosquitoes that attempt to bite them, before penetration or injection of saliva if possible. Moreover, a stopping rule instructs subjects to cover any treated skin immediately if more than one mosquito attempts to bite during any exposure period. Subjects will be exposing small areas of treated skin for only 4 minutes per hour. Other parts of the body will be protected with provided gloves, headnets and full body suits made of Tyvek, through which mosquitoes do not bite. Subjects will be teamed with a partner for joint observation and experienced technical personnel will be present at all times for assistance.

The US Centers for Disease Control estimates that about 1-in-5 people who become infected with West Nile virus will develop West Nile fever. Subjects are instructed to be alert for any flu-like symptoms (unusual tiredness or unusually severe headaches, body aches, fever), glandular swelling or a rash on the trunk of the body, for up to two weeks after the test. About 1-in-150 infected people will develop more serious symptoms, which will be described to the subjects. Most people (about 4 out of 5) who are infected with West Nile virus will not develop any type of illness.

In addition, the techniques employed to minimize exposure to mosquitoes and mosquito bites render the possibility of contracting a disease carried by mosquitoes very low. Field tests are being conducted in an area where such viruses have not been detected by county and state health or vector/mosquito control agencies for at least a month, so the risk is probably low that any individual mosquito present carries a disease. In each trial, only two experienced, qualified subjects (qualification criteria described in §9.1) will expose untreated limbs to monitor biting pressure, at the same infrequent, brief intervals as treated subjects, and with multiple assistants to remove any mosquitoes that lite with intent to bite.

In summary, the combination of technical precautions and natural factors means that the chances that any subject will contract West Nile fever or another disease from a mosquito bite are extremely small. There is probably no more risk to subjects than they would experience when engaged in normal outdoor activities in a similar rural area at the same time of year. If at anytime during the study a subject suffers a skin reaction or feels ill, he or she is instructed to inform the Study Director (i.e., the 'Principal Investigator'), or anyone else who is also working to direct the study. Such subjects will be immediately withdrawn from testing and medical management will be implemented (§9.5). Subjects may also request access to standard first aid materials (such as bandages, antiseptics, and mild topical and oral antihistamines) and request qualified first aid assistance at any time. Epi-Pens will also be onsite in case of a Type 1 (anaphylactic) allergic reaction. At least one qualified researcher will remain with the other test subjects if other researchers depart with an injured or ill subject. Subjects are clearly and repeatedly informed that they may remove themselves for any reason from the study at any time, without penalty to their compensation.

Against these slight risks are balanced substantial and reasonably likely benefits. Insect-borne disease is of growing significance in the United States and around the world where U.S. citizens are active. Moreover, discomfort associated with nuisance biting restricts many work and pleasure activities. Because EPA registration requires efficacy data, a test such as that proposed here is the only path toward further product development and greater availability of new KBR 3023 mosquito repellents to consumers in the United States.

5.5 Standards Applied:

U. S. EPA Good Laboratory Practice Regulations (40 CFR 160); 40 CFR 26 subparts K and L; FIFRA § 12(a)(2)(P); California State EPA Department of Pesticide Regulation study monitoring (California Code of Regulations Title 3, Section 6710).

6 INVESTIGATIONAL AND TEST MATERIAL CONTROL:

6.1 Test Substance:

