6.1.1 Description of the Test Materials

There are two test materials, a 20% KBR 3023 lotion ('cream') and a 20% KBR 3023 pump spray. Labels are appended.

6.1.2 Trade Name:

KBR 3023 All-Family Insect Repellent Cream KBR 3023 All-Family Insect Repellent Spray

6.1.3 Dosage Form:

Lotion and Pump Spray applied to the skin.

6.1.4 Dose:

Determining dosage is part of the main objective of this study. Dosage for repellency testing will be the mean of the subject means determined for each product in the dosimetry portion of this study. Dosage will be measured in weight and reported by weight and volume.

6.1.5 Manufacturing Site:

Laboratory-prepared by Saltigo GmbH, (Lanxess Group), Germany.

6.1.6 Test Material Storage During Study:

Prior to application, the test materials will be stored indoors, at room temperature and away from direct sunlight or direct sources of moisture or the conditions specified by the sponsor. Storage will be at Carroll-Loye Biological Research.

6.1.7 Test Material Safety:

EPA regulates use of inert ingredients (also termed "other" ingredients) by toxicology profiles in animal tests and by their inclusion in EPA lists of "approved" other ingredients. Ingredients on lists 4a or 4b are considered relatively safe for all uses. The ingredients in the proposed insect repellent formulations are mainly on lists 4a or 4b with a few ingredients on list 3 because of ocular irritation potential. EPA normally regulates the presence of materials on list 3 by labeling to avoid contact with eyes or to prohibit application by children. The other ingredients in the test formulations are commonly used in marketed products for application to human skin as components of cosmetic and drug formulations.

The insect repellent products proposed for testing has been tested in animals for potential oral and dermal toxicity. The active ingredient (KBR 3023) has an extensive toxicity data file, has been previously registered by EPA, and has a positive safety record in consumer use.

A toxicology profile of KBR 3023 is provided in the appendices.

6.1.8 Test Material Composition and Stability:

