9.1.2. Inclusion criteria specific to the two untreated subjects

9.1.2.1 To qualify for candidacy as a subject who exposes untreated skin, an individual must be regarded as competent to do so by the Principal Investigator, must have participated in at least five prior Carroll-Loye repellent efficacy trials, or have participated in at least three such trials and have at least two years of experience as a college life sciences major, or be professionally employed in vector control services.

9.1.3 Exclusion criteria, all subjects:

- 9.1.3.1 Known to be hypersensitive to mosquito bites or exhibiting hypersensitivity during test
- 9.1.3.2 Known to be sensitive or showing sensitivity to any of the test product ingredients, after application.
- 9.1.3.3 Poor physical condition.
- 9.1.3.4 Unwilling to submit to brief query about personal condition.
- 9.1.3.5 Use of insect repellent within one day preceding the study.
- 9.1.3.6 Unwilling to refrain from use of perfumed products, alcoholic beverages or smoking after 9 PM the evening preceding the test and throughout the test.
- 9.1.3.7 Known to be pregnant or lactating. Pregnancy will be self-checked by each female volunteer on the morning of the repellent test using an OTC test kit provided by the Study Director. Results of each such test will be immediately verified by direct inspection by a female technician trained to make that assessment. Only volunteers scored as nonpregnant will be allowed to participate.
- 9.1.3.8 Unable to deliver the test materials to own left and right limbs.
- 9.1.3.9 Unable to see mosquitoes on skin or otherwise effectively monitor and remove mosquitoes that alight on skin.
- 9.1.3.10 Student or employee of the Study Director.
- 9.1.3.11 Does not regularly spend time in outdoor settings.
- 9.1.3.12 Withdraws from testing before receiving a confirming LIBe, when the total exposure duration is less than 90% of the mean of subjects who did not withdraw, and when not more than 2 of 10 subjects have so withdrawn.

If more that 2 of 10 subjects withdraw prematurely, those with the briefest participation will be replaced first. This exclusion factor is not automatically invoked if the Study Director ends exposures due to other factors, such as darkness; in such cases the data collected before termination may be sufficient to meet the study goals.

9.1.4 Number of Subjects and Rationale for Sample Sizes:

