9.1.6.3 Screening of Candidate Subjects

All such potential participants are screened or re-screened for suitability for each test in a private, one-on-one conversation with the Study Director. Some former subjects have been excluded from mosquito repellent testing, for example, because they passed the upper age limit, when the health risks of West Nile Fever are statistically more serious. The Exclusion Criteria (section 9.1.2) are exercised by asking each candidate to address them in the interview with the Study Director. It is explained to female candidates that pregnancy will be assessed directly on the test day. The Study Director encourages candidates to ask questions and ask for clarification at any time during the interview and in all activities that follow. To candidates that pass screening, the Study Director describes the test purpose in plain language (in English), and the procedures and comportment to be followed are described. Candidates are then asked if they would like to retire from consideration at that point. If they wish to remain in consideration, it is emphasized that they may withdraw from the test at any time during the test without penalty to their compensation. This freedom is especially re-emphasized in cases in which considerable effort or expense has been required to include a subject (e.g., travel to a distant site), to discourage the conception that that effort or expense creates any added obligation in the subject.

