After you have completed an application successfully, wash and dry the treated arm so that none of the repellent you have applied is visible on close inspection. You will continue until you have completed three successful applications. You may then repeat the entire procedure above, but with the lower leg."

1. Study subjects
d. Dosimetry (lotion only)
i. practice
ii. performance
(v. 1, 1 December 2006)

KBR 3023 Insect Repellent Cream

Contains Bayrepel[™]. Long-lasting, effective protection from mosquitoes ticks, biting flies, and fleas. Not oily, greasy or sticky. It smells great, too. Repels insects for up to 8 hours.

ACTIVE INGREDIENT: Picaridin, 1-Methylpropyl-2-(2-hydroxyethyl)-1-piperidine carboxylate	- 20%
INERT INGREDIENTS**	-000/
TOTAL	100.0%

**Other Ingredients: Purified water, glycerin, denatured alcohol, thickener, emollient, fragrance

KEEP OUT OF REACH OF CHILDREN WARNING

STOP – Read This Entire Label Before Use

PRECAUTIONARY STATEMENTS

WARNING. HAZARDS TO HUMANS.

Causes substantial but temporary eye injury. Do not get in eyes. Wash thoroughly with soap and water after handling, returning indoors, and before eating, drinking, chewing gum, or using tobacco. Discontinue use and consult a doctor if irritation or rash occurs.

The information below describes the first aid procedures for incidents involving KBR 3023 Insect Repellent Cream:

FIRST AID

IF IN EYES:

١

- Hold eye open and rinse gently with water for 15-20 minutes.
- Remove contact lenses, if present, after the first five minutes, then continue rinsing.
- Call a poison control center or doctor for treatment advice.

IF SWALLOWED:

- Call a physician or poison control center immediately for treatment advice.
- Have person sip a glass of water if able to swallow.
- Do not induce vomiting unless told to do so by a Poison Control Center or a doctor.
- Do not give anything to an unconscious person.

Have the product container or label with you when calling a poison control center or doctor or going for treatment. You may also contact [name] for emergency medical information.

The LANXESS Pittsburgh Emergency Response Telephone Number is [contact]

IN CASE OF EMERGENCY, CALL: CHEMTREC [contact] EPA REGISTRATION NUMBER: 39967-50 EPA ESTABLISHMENT NUMBER:

INTERNATIONAL [contact] Net Contents: Lot No.:

LANXESS Corporation [name] ● [name]

LABEL TEXT DATE: 12/19/06

PHYSICAL HAZARDS

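### The risk section (5.4) claims a broader allergy exclusion than the exclusion list (9.1.3.2) that is put to candidates at screening; the two must be reconciled

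*Protocol*

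**What the plan says.** Section 5.4 (Balance of Risks and Benefits) gives several reasons why exposure to the test materials carries little risk. One is an enrolment rule: "Subjects with known allergic reactions to insect repellents and common cosmetics are excluded from participating".

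Section 9.1.3 lists the exclusion criteria for all subjects, numbered 9.1.3.1 to 9.1.3.12. The item closest to the rule in 5.4 is 9.1.3.2: "Known to be sensitive or showing sensitivity to any of the test product ingredients, after application".

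Section 9.1.6.3 describes how the list is used: "The Exclusion Criteria (section 9.1.2) are exercised by asking each candidate to address them in the interview with the Study Director". The consenting procedures in the IRB site questionnaire describe the interview in almost the same terms and give the same section number. That number is wrong in both places: 9.1.2 holds the inclusion criteria for the two untreated subjects, and the exclusions are in 9.1.3.

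**The concern.** The two sections define the excluded group differently. Section 5.4 defines it by a history of reacting to a class of products: repellents and ordinary cosmetics. Criterion 9.1.3.2 defines it by sensitivity to the particular ingredients of the cream and the spray. If the interview follows the list, the broader question in 5.4 need never be asked.

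At stake is subject protection and the accuracy of the risk statement. According to its introductory page, the protocol was approved by the IRB and assembled for review by EPA and its Human Studies Review Board. Those readers were told of a safeguard that the written screening step does not fully deliver.

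**Working it through.** No arithmetic applies. The check is whether any criterion put to candidates has the scope claimed in 5.4.

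**Step 1. Compare the list with 5.4.**

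- 9.1.3.1 is about insect bites: "Known to be hypersensitive to mosquito bites or exhibiting hypersensitivity during test". It does not concern repellents or cosmetics.
- 9.1.3.2 is about test product ingredients. It overlaps with 5.4 but is narrower.
- 9.1.3.5 is the only item that names insect repellent: "Use of insect repellent within one day preceding the study". It concerns recent use, not allergy.
- 9.1.3.6 is the only item that touches scented products: "Unwilling to refrain from use of perfumed products, alcoholic beverages or smoking after 9 PM the evening preceding the test". It concerns willingness to abstain, not allergy.
- The remaining eight items cover physical condition, willingness to be questioned, pregnancy and lactation, ability to apply the product, ability to see and remove mosquitoes, dependence on the Study Director, time spent outdoors, and early withdrawal. None concerns allergy.

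Result: 0 of 12 criteria match the scope of 5.4, and 1 of 12 (9.1.3.2) covers part of it. The inclusion criteria in 9.1.1 and 9.1.2 add nothing on allergy.

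**Step 2. Find how much 9.1.3.2 covers.** The test product ingredients are the repellent active plus other ingredients that 6.1.7 calls "commonly used in marketed products for application to human skin as components of cosmetic and drug formulations". So 9.1.3.2 catches known sensitivity to KBR 3023 and to any cosmetic ingredient that is also in the cream or spray. It leaves out:

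- a known allergy to a different repellent, where the cause is not an ingredient of the test products;
- a known allergy to a cosmetic that shares no ingredient with them.

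Both kinds of candidate fall within the wording of 5.4 and outside the list.

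**Step 3. See which text governs at screening.** Section 9.1.6.3 and the site questionnaire both say that the exclusion criteria are what each candidate is asked to address. Neither refers to 5.4. Both direct the interviewer to a section that is not the exclusion list.

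**Step 4. Use 5.4's other known-reaction exclusion as a benchmark.** The next paragraph of 5.4 says that people aware of a history of reacting to mosquito bites are excluded. That statement has a matching list item, 9.1.3.1. So the section evidently intends its exclusions to be applied, and the repellent-and-cosmetic exclusion is the one without a counterpart of equal breadth.

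**Step 5. Count who is screened this way.** Under 8.3.2 each field trial has 10 + 10 = 20 treated places. There are two trials, so 2 × 20 = 40 treated places. Dosimetry adds 10 places per product, so 2 × 10 = 20. These are places rather than people, because 5.2 allows dosimetry subjects to go on to efficacy testing. The counts show how widely the list is used, not how many candidates would be affected.

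**The case against.** The strongest reply is that the allergies that matter most are already excluded. Criterion 9.1.3.2 bars anyone known to be sensitive to the active or to any other ingredient of either product. This stands. A reader might infer from 5.4 and 9.1.3 together that the list has no allergy criterion for the products, so that allergic people can freely be enrolled. The documents do not support that: the list has a narrower criterion, not none.

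Second, 5.4 is itself protocol text, the Study Director interviews every candidate alone, and 9.1.6.3 lets the Study Director refuse anyone. The consent form was not among the pages available, so it may repeat the broader exclusion. These points make wrongful enrolment less certain. They do not remove the mismatch, because unspecified discretion does not require the broader question to be asked.

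Third, the low-risk conclusion does not rest on this exclusion alone. The appended toxicology profile reports no skin irritation or sensitisation in animal studies, and first contact is with people who have taken part in earlier repellent tests at this site. That limits the seriousness of the gap.

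Two further inferences are tempting and should not be drawn.

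- A reader might argue that candidates cannot apply 9.1.3.2, because the cream label names some ingredients only by class ("Purified water, glycerin, denatured alcohol, thickener, emollient, fragrance") and the spray label as reproduced shows no ingredient list. The missing spray list may be a loss in reproduction, and a consumer label does not show what the interviewer knows about the formulation.
- A reader might argue that each subject who reacts is a lost replicate. Section 9.1.8 enrols three extra subjects and allows alternates to replace some withdrawals, and 9.1.3.12 has a replacement rule. No loss of sample can be derived from this mismatch.

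**Conclusion.** The point holds as an inconsistency between the risk statement and the enrolment rules. Section 5.4 claims a broader allergy exclusion than 9.1.3.2 provides, and no other criterion closes the gap. The cross-reference to 9.1.2 in 9.1.6.3 and in the site questionnaire is a second, plain error.

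The size is modest. The uncovered group is limited to candidates with a known allergy to another repellent, or to a cosmetic with no ingredient in common with the test products. Their number cannot be derived from the protocol. The conclusion assumes that the interview follows the written list, as 9.1.6.3 says, and that nothing in the consent form restores the broader exclusion. It should be put right before enrolment because it concerns a stated protection and is cheap to correct. Which of the two exclusions is the right one is not judged here.

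**What to change.** Reconcile 5.4 and 9.1.3.2, so that the risk statement and the list used at interview give the same allergy exclusion in the same terms. The sponsor and the Study Director must decide which scope is intended. If the approved consent form mentions the exclusion, check that it agrees.

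Correct the reference to the exclusion criteria from 9.1.2 to 9.1.3, both in 9.1.6.3 and in the consenting procedures of the IRB site questionnaire.

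No change to the stop rule in 9.5 is needed for this point, and neither is any extension beyond allergic reactions.

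The cost is a short text amendment. If the broader scope is kept, a few of the 58 people in the volunteer database may become ineligible. Sample size and analysis do not change.
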